5.3 Treatment Duration

While patients are expected to receive study treatment for approximately 1 year, those seeing clinical benefit may stay on treatment for an additional year.

Patients will be followed for survival for 1 year after the last dose of study drug. The total duration of the study is planned to be at least 3½ years.

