5.1 Main Treatment Periods

Patients who taper off study treatment and all immunosuppressive therapy due to achieving a cGVHD status of CR or PR will continue to be followed according to the Schedule of Assessments (Appendix D), including all safety and efficacy assessments, and will be monitored for cGVHD recurrence.

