6.6.2 Survival Follow Up (Every 3 Months [\pm 30 Days])

Patients who permanently discontinue the study treatment for reasons other than achieving a GVHD status of CR or PR will be followed for survival, relapse of underlying malignancy, and reporting of new cGVHD therapies approximately every 3 months for 1-year after completion of study drug, and can be contacted by telephone, email, or by a site visit.

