10.4.2 Efficacy Analysis

All efficacy analyses will be performed using the Response Evaluable Analysis Set.

- ORR is defined as the proportion of patients with a cGVHD status of CR or PR after 6 months of treatment according to the NIH Consensus Criteria (Lee et al. 2015).
- Overall Survival (OS) is defined as the time from the first day of study drug administration (Day 1) to death on study. Patients who are alive will be censored at the date of last known date alive.

For ORR, the estimates and the associated 95% CIs (based on the Clopper-Pearson method) will be calculated.

For OS, a Kaplan-Meier curve will be generated and the median time to event and the associated 95% CIs will be provided.

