Appendix D: BMT 29 Schedule of Assessments

Study Period	Screening	Treatment Period							Follow-Up		
		Cycle 1				Cycles 2 to 6	Cycle 7	Cycles 8+			
Cycle ^a											
Visit Day	Day -28 to -1 ^b	1	8	15	22	1 (± 7 days)	1 (± 7 days)	1 (± 7 days)		(± 7 days)	Every 3 months (± 1 month)
Informed consent	X										
Inclusion / exclusion criteria	X										
Medical history and demographics ^c	X										
Physical examination ^{c,d}	X	X	X	X	X	X	X	X	X	X	
ECOG performance status ^{c,d}	X	X				X	X	X	X	X	
Vital signs ^c	X	X	X	X	X	X	X	X	X	X	
Blood transfusion review ^d	X	X				X	X	X	X		
12-Lead electrocardiogram ^c	X								X		
Pulmonary function test ^d	X					X (C4 only)	X				
Urine pregnancy test ^{c,e}	X	X				X	X	X	X	X	
Safety laboratory (hematology, lipids [fasting], and chemistries) ^c	X	X	X	X	X	X	X	X	X	X	
Safety laboratory (urine) ^c	X	X	X	X	X	X	X	X	X	X	
Virology testing ^f	X										
Concomitant medication review	X	X	X	X	X	X	X	X	X	X	
Adverse events and infection monitoring	X	X	X	X	X	X	X	X	X	X	
cGVHD diagnosis and staging	X										
Clinician-reported global cGVHD activity assessment ^g		X				X	X	X	X		

CONFIDENTIAL

INNOVATIONS STUDY NUMBER: BMT 29

VERSION 4

STUDY DRUG: INCB039110 (ITACITINIB)
FINAL PROTOCOL DATE: 26 OCTOBER 2021

Study Period	Screening	Treatment Period						Follow-Up		
		Cycle 1			Cycles 2 to 6	Cycle 7	Cycles 8+	EOT ^k	30-Day Safety FU ^l	FU for Survival ^m
Cycle ^a		1	8	15	22	1 (± 7 days)	1 (± 7 days)	1 (± 7 days)	(± 7 days)	Every 3 months (± 1 month)
Visit Day	Day -28 to -1 ^b									
Patient-reported global cGVHD activity assessment ^g		X				X	X	X	X	
Assessment of cGVHD response (NIH criteria) ^h						X	X	X ^h	X	
Chimerism assessment (institutional standards)	X									
Lee Symptom Scale ⁱ	X	X					X		X	
Document corticosteroid dosage (total dose/kg and type of corticosteroid)	X	X	X	X	X	X	X	X	X	
Document concomitant cGVHD therapies	X	X	X	X	X	X	X	X	X	
Assess underlying disease relapse ^j		X				X	X	X	X	X
New cGVHD therapies										X X
Dispense/collect study drug		X				X	X	X	X	
Patient status										X

Itacitinib Schedule of Assessments Footnotes

- a Treatment cycles are 28 days (4 weeks). Patients will continue treatment with itacitinib for up to 24 months or until patients discontinue from study treatment for any of the following reasons listed in Section 3.3.
- b Screening should take place within 28 days of start of study treatment.

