- j Participants will be closely monitored for any evidence of underlying disease relapse or recurrence on Day 1 of each cycle, at the EOT, and the survival follow-up visit. A formal re-staging is not required. Re-staging will be done at the Investigator's discretion. The date of malignant and non-malignant hematologic disease relapse and subsequent management should be collected on the appropriate eCRF.
- k An EOT visit should be performed for all patients who permanently discontinue study treatment (preferably within 7 days and no later than 14 days after the last treatment of study drug). If the EOT visit coincides with a regular study visit, the EOT evaluations will supersede those of that scheduled visit, and the data should be entered in the EOT visit in the eCRF (see Section 6.5).
- l A safety follow-up visit will be done 30 days (± 7 days) following end of treatment. Adverse events and SAEs must be reported for least 30 days after the last dose of study drug, and must be followed until toxicities resolve, return to baseline, or are deemed irreversible, whichever is longer (see Section 6.6.1).
- m Follow-up for survival: patients will be followed for survival after treatment has been discontinued. Patients should be contacted by telephone, email, or visit every 3 months for 1-year after their last dose of study treatment to assess for new GVHD therapy, relapse of underlying malignancy and survival status until death, withdrawal of consent, or the end of the study, whichever occurs first (see Section 6.6.2).

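### Survival contact ends 1 year after each patient's last dose while OS runs from Day 1, so after about 12 months censoring depends on when and why treatment stopped and is likely informative

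*Combined protocol and SAP*

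**What the plan says.** **Length of follow-up.** Section 5.3: "Patients will be followed for survival for 1 year after the last dose of study drug". Appendix D footnote m: "Patients should be contacted by telephone, email, or visit every 3 months for 1-year after their last dose of study treatment", to run "until death, withdrawal of consent, or the end of the study, whichever occurs first". Section 6.6.2 uses the same one-year period and describes who enters it: "Patients who permanently discontinue the study treatment for reasons other than achieving a GVHD status of CR or PR will be followed for survival". Section 5.1 keeps responders who taper off all therapy on the visit schedule: they "will continue to be followed according to the Schedule of Assessments (Appendix D), including all safety and efficacy assessments".

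**Length of treatment.** Section 5.3 expects about 1 year of drug, with a second year for patients who are benefiting. Appendix D footnote a sets the ceiling: "Patients will continue treatment with itacitinib for up to 24 months".

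**Analysis.** Section 10.4.2 defines OS from the first dose to death on study and adds: "Patients who are alive will be censored at the date of last known date alive". It specifies a Kaplan-Meier curve and a median with 95% CI. It gives no common survival cut-off, landmark or numbers at risk, and no handling of censoring related to prognosis.

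**The concern.** The OS clock starts at Day 1, but the contact schedule is counted from the last dose. How long a survivor stays in the risk set therefore depends largely on how long that patient stayed on drug. Time on drug is linked to outcome: Section 3.3 stops patients for malignancy relapse, intolerable toxicity, intercurrent illness, and GVHD that needs more systemic therapy, while Section 5.3 reserves the second year for those who benefit.

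Kaplan-Meier needs censored patients to have the same later death hazard as those still followed. Here survivors among the early stoppers leave first, and nothing in the plan adjusts for it. OS is a stated secondary objective, so the reported curve beyond the first year is at stake. The primary endpoint is not.

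**Working it through.** **1. The plan's own figure.** The only design figure is the CI width for ORR in Section 10.2. With 8 of 40 responders, the Clopper-Pearson limits are the 0.025 quantile of Beta(8, 33) = 0.0905 and the 0.975 quantile of Beta(9, 32) = 0.3565. The width is 0.2660, which reproduces 0.266. No OS figure, mortality rate or dropout rate is given, so any size for the OS effect rests on assumptions.

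**2. When survivors are censored.** Censoring month = stopping month + 12.

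| Last dose (month) | Scheduled contact ends (month from Day 1) |
|---|---|
| 1 | 13 |
| 2 | 14 |
| 6 | 18 |
| 12 | 24 |
| 24 | 36 |

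OS is analysed in the Response Evaluable Analysis Set (Sections 10.3 and 10.4.2), which requires at least one 28-day cycle. The rule first bites at 28 + 365 = 393 days, about month 13. With the 30-day contact window it could bite at 393 − 30 = 363 days. Up to about 12 months the curve is unaffected by this rule.

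**3. What decides the direction.** After month 12, the Kaplan-Meier hazard comes only from patients still under contact. There are three cases:

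- Early stoppers keep a higher hazard more than a year after stopping. Their later deaths are missed, and the curve is too high.
- Stopping does not change the hazard. There is no bias.
- The excess hazard is confined to the followed year. Patients in their high-risk year are still counted, while earlier stoppers who have passed through it are already censored, so the curve can be too low.

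**4. Size under assumptions.** These inputs are assumed here and are not in the documents:

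- on-treatment survival of 90% per year, so a monthly hazard of −ln(0.90)/12 = 0.0088;
- exponential stopping times with a 1-month minimum and 20%, 40% or 60% stopped by month 6;
- half of those still on drug at month 12 continuing to month 24.

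One million patients were simulated per scenario, with censoring at last dose + 12 months. Bias is Kaplan-Meier minus true OS, in percentage points.

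| Hazard after an early stop | 12 mo | 18 mo | 24 mo | 30 mo |
|---|---|---|---|---|
| Unchanged | 0.0 | about 0 | about 0 | about 0 |
| Lasting, ratio 2 to 5 | 0.0 | +0.3 to +1.1 | +1.1 to +4.1 | +1.7 to +4.9 |
| Ratio 3 or 5, ending 3 to 12 months after the stop (40% stopped by month 6) | 0.0 | −0.1 to −1.2 | −0.4 to −3.1 | −0.5 to −7.1 |

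**5. Numbers at risk.** With 40% stopped by month 6, about 18 to 20 of 40 are at risk at month 18, about 11 to 12 at month 24, and about 3 at month 30.

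**6. Effect of a common end point.** With everyone followed to month 24 from Day 1, the estimate equals true OS at 12, 18 and 24 months in every scenario. For example, with 40% stopped by month 6 and a lasting ratio of 3, 24-month OS is 0.653 both in truth and after the change, against 0.680 under the protocol's rule.

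**7. The median.** In 16 of the 18 scenarios true OS stays above 50% through month 30. The other two pair a lasting fivefold hazard with 40% or 60% stopping by month 6. In them true OS at month 30 is 0.450 and 0.367, with about 3 and 1 of 40 at risk.

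**The case against.** A reader might infer that the OS curve is biased upward, so that 24- and 36-month survival and any median come out too favourable. A simple two-group model seems to support this. Let 30% stop at month 2 with a monthly hazard of 0.03, and let the rest stay on drug to month 24 with a hazard of 0.005. At month 14, S = 0.3·exp(−0.42) + 0.7·exp(−0.07) = 0.850. The Kaplan-Meier limit at month 36 is 0.850·exp(−0.11) = 76.1%, against a true 0.3·exp(−1.08) + 0.7·exp(−0.18) = 68.7%. With 50% stopping early, the figures are 71.2% and 58.7%.

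The documents do not support that reading:

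- It builds in an excess hazard that never ends, and the plan contains no mortality data. If the excess ends 12 months after stopping, the same model gives zero bias at 24 and 36 months.
- It keeps every later stopper on drug to month 24, although Sections 5 and 5.3 expect about 12 months.
- True OS never falls below 58.7% in it, so it says nothing about the median.

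Other points also count against the concern. Responders who taper off stay on the full visit schedule (Section 5.1), so time on drug is not the only determinant of follow-up. Section 3.3 also lists patient request, non-compliance and pregnancy, which need not carry mortality risk. This is an exploratory single-arm pilot of 40 with no hypothesis test, and OS is descriptive. Ignoring censoring, the 95% half-width at a true 24-month OS of 0.653 is 1.96·√(0.653·0.347/40) = 14.8 points, larger than any bias at 24 months in the scenarios above.

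These points remove the claim of a known direction and lower the priority. They do not remove the dependence of censoring on outcome. They also do not let the trial's own data settle the sign, because the deaths that would do so occur after scheduled contact ends.

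**Conclusion.** The point holds with its direction left open. Three sections tie survival contact to the last dose, OS is timed from Day 1, and the reasons for stopping early or continuing are linked to prognosis. Censoring after about 12 months is therefore likely informative, and the plan does not address it.

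Up to about 12 months the rule has no effect. At 24 months OS is probably overstated, by about 1 to 4 points, if early stoppers have lasting worse survival. It is unbiased if their hazard does not differ. It is understated in the simulated scenarios, by 0.4 to 3.1 points, if the excess falls within the followed year. All these sizes depend on the assumed stopping pattern and hazards. Lasting excess is plausible after relapse or uncontrolled GVHD, but the documents do not show it.

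No effect on the median is established, since nothing in the documents places the median within follow-up. The primary ORR and its CI are untouched. This is a low-cost improvement to a secondary endpoint.

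**What to change.** **Analysis wording (Section 10.4.2).** Make OS at 12 months from Day 1 the headline OS estimate. Show numbers at risk under the curve, report follow-up by reverse Kaplan-Meier, and mark the curve beyond 12 months as subject to informative censoring. This needs no new data. The cost is a shorter headline period.

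**Preferably also (Sections 5.3 and 6.6.2, Appendix D footnote m).** Continue the existing 3-monthly telephone or email status contact for every treated patient to a common time from Day 1, whatever the last-dose date. Month 24 is a natural choice, because patients who complete 12 months of drug are already followed that far. The unflagged curve could then run to month 24. Beyond that the warning still applies, since only patients treated for longer are followed.

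**Cost.** A patient who stops at month 2 needs (24 − 14)/3, or about 3 to 4, further contacts; one who stops at month 6 needs (24 − 18)/3 = 2. The change also needs an amendment with IRB approval (Section 14.1). The resulting OS curve may be less favourable than the one the present rule would give.

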5.4 Concomitant Medications

Patients will be instructed not to take any additional medications during the course of the study without prior consultation with the research team. At each visit, the patient will be asked about any new medications he/she is taking or has taken after the start of the study drug.

5.4.1 Permitted Concomitant Medications

Patients who undergo allo-HSCT are at risk for a variety of infections based on the degree of immunosuppression induced by the conditioning regimen before transplant. As such, it is considered routine practice to use antibiotics, anti-infectives, and immunizations as prophylactic therapies (Tomblyn et al. 2009). In cases where post-transplant anti-infective prophylaxis

CONFIDENTIAL

STUDY DRUG: INCB039110 (ITACITINIB)
FINAL PROTOCOL DATE: 26 OCTOBER 2021

INNOVATIONS STUDY NUMBER: BMT 29
VERSION 4

measures are necessary, ongoing therapy may continue at the Investigator's discretion per institutional guidelines.

Additional supportive care measures (e.g., use of antimotility agents for diarrhea management, topical steroids) are permitted at the Investigator's discretion. Concomitant treatments and/or procedures that are required to manage a patient's medical condition during the study will be recorded in the eCRF.

5.4.2 Restricted Concomitant Medications

The following medications have restrictions on use during the treatment period of the study:

- Medications that interfere with coagulation or platelet function including, but not limited to, aspirin in doses exceeding 81 mg/day and related drugs such as heparin and warfarin sodium (Coumadin®) are not permitted. Low-dose aspirin (≤ 81 mg per day) is permitted, unless clinically contraindicated, as is the use of low molecular weight heparin. If concomitant administration of an anticoagulant/antiplatelet medication is indicated, then caution and enhanced monitoring is required; it is suggested that CBCs be checked every 1 to 2 weeks for the first 2 cycles of administration. History of thrombocytopenia should be a factor in the choice of anticoagulant and dose.
- For coadministration with potent CYP3A inhibitors; consider alternative agents with less CYP3A inhibition (Appendix J). Differences in individual sensitivity and varied CYP enzyme inhibition may result in the need for dose reduction of itacitinib and/or corticosteroids, as appropriate. **Note:** If the participant's medical condition requires treatment with any of these drugs, a dose reduction of itacitinib to 100 mg QD is recommended, as more potent inhibitors have been shown to increase exposure to itacitinib. No dose adjustment is recommended for concomitant administration of other CYP3A4 inhibitors.
- Coadministration with CYP3A4 inducers (Appendix J).

5.4.3 Prohibited Concomitant Medications

The following treatments are prohibited during the treatment period of the study:

- No other investigational therapy (e.g., chemotherapy, radiation therapy, surgery, immunotherapy [including other JAK inhibitors], biologic therapy, hormonal therapy, or tumor embolization) should be given to patients to treat a suspected malignancy relapse. If such agents are required for a patient, then the patient must first be withdrawn from the study.
- Herbal preparations/medications are not allowed throughout the study. These herbal medications include, but are not limited to: St. John's wort, kava, ephedra (ma huang), gingko biloba, dehydroepiandrosterone (DHEA), yohimbe, saw palmetto, and ginseng. Patients should stop using these herbal medications 7 days prior to first dose of study drug.

CONFIDENTIAL

STUDY DRUG: INCB039110 (ITACITINIB)
FINAL PROTOCOL DATE: 26 OCTOBER 2021

INNOVATIONS STUDY NUMBER: BMT 29
VERSION 4

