3.3 Discontinuation from Study Treatment

Patients will be discontinued from study treatment for any of the following reasons:

- Relapse of underlying malignancy
- Irreversible or intolerable toxicity or abnormal laboratory values thought to be related to drug toxicity
- The patient is unable to tolerate itacitinib at a dose of 100 mg QD.
- Additional systemic therapy is required for GVHD progression or lack of response, including corticosteroid doses greater than those used on Study Day 1.
- Conditions requiring therapeutic intervention not permitted by the protocol
- Intercurrent illness (this will be at the Investigator's discretion)
- Inability of the patient to comply with study requirements
- Patient requests to discontinue treatment, but agrees to finish study procedures
- Patient withdraws consent from the study and is discontinued from the study
- Non-compliance/lost to follow-up
- Pregnancy
- Further participation would be injurious to the patient's health or well-being, in the Investigator's medical judgment.
- The study is terminated by the Sponsor or the Institutional Review Board (IRB).

After discontinuation from protocol treatment, patients must be followed for AEs for 30 days after their last dose of study drug. All new AEs occurring during this period must be reported and followed until resolution, unless, in the opinion of the Investigator, these values are not likely to improve, because of the underlying disease. In this case, the Investigator must record his or her reasoning for this decision in the patients' medical records.

All patients who have Grade 3 or 4 laboratory abnormalities (per National Cancer Institute Common Terminology Criteria for Adverse Events [NCI CTCAE] Version 5) at the time of discontinuation must be followed until the laboratory values have returned to Grade 1 or 2, unless it is, in the opinion of the Investigator, not likely that these values will improve. In this case, the Investigator must record his or her reasoning for making this decision in the patients' medical records.

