6.4 Response Assessments

Response criteria (CR, PR, or other [unchanged, mixed response, progression]) based on the 2014 NIH Consensus Development Project on Clinical Trials in cGVHD (see Appendix H for criteria) will be assessed on Day 1 of Cycles 2 through 7; and then every odd-numbered cycle thereafter starting on Day 1 of Cycle 9, as well as the EOT visit.

Patients with GVHD progression, progression of the underlying malignancy, or unacceptable toxicity should be discontinued from the study; patients with stable GVHD or a GVHD response to therapy will continue treatment.

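### Study-exit wording in Sections 5.4.3 and 6.4, with an OS event limited to undefined on-study deaths, could bias overall survival upward

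*Combined protocol and SAP*

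**What the plan says.** Two sections take patients out of the study. Section 5.4.3, on patients who need prohibited therapy for a suspected malignancy relapse, says: "If such agents are required for a patient, then the patient must first be withdrawn from the study". Section 6.4 says: "Patients with GVHD progression, progression of the underlying malignancy, or unacceptable toxicity should be discontinued from the study".

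Other sections take them off treatment only. The list in Section 3.3 opens: "Patients will be discontinued from study treatment for any of the following reasons". It includes malignancy relapse, intolerable toxicity, and GVHD progression that needs additional systemic therapy. The one item on the list that also ends study participation is: "Patient withdraws consent from the study and is discontinued from the study". Section 6.5 gives GVHD progression, malignancy progression and unacceptable toxicity as reasons why treatment ends, with an end-of-treatment visit.

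Under Section 6.6.2, patients who stop treatment permanently for reasons other than a complete or partial response "will be followed for survival, relapse of underlying malignancy, and reporting of new cGVHD therapies approximately every 3 months for 1-year". Section 5.3 sets the same 1-year period after the last dose. Appendix D footnote m ends this follow-up only at death, withdrawal of consent or the end of the study.

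Section 10.4.2 defines OS as "time from the first day of study drug administration (Day 1) to death on study", and adds: "Patients who are alive will be censored at the date of last known date alive".

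**The concern.** A site that takes Sections 5.4.3 and 6.4 at their word would close the patient out. A site that follows Section 6.6.2 would keep contacting the same patient every 3 months. It cannot do both.

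The OS definition adds a second route to the same loss. The protocol does not define *on study*. Section 11.3.4 sets on-study deaths apart from deaths in what it calls post-study survival follow-up. Even with complete follow-up, an analyst could leave the later deaths out. The censoring rule does not settle the matter: a patient who died in survival follow-up is not alive, yet may not count as a death on study.

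Relapse, progression and toxicity plausibly carry a higher risk of death. If follow-up or counting stopped at these events, censoring would be informative and Kaplan-Meier OS too high. With a single arm, no control group carries the same error, so it would not cancel.

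**Working it through.** **1. The plan's own figures.** The documents give no survival rate, event count or precision for OS, so there is nothing to reproduce for this endpoint. The only design figure is the confidence-interval width for the response rate (Section 10.2). With 8 responders of 40, the Clopper-Pearson interval is 0.0905 to 0.3565, a width of 0.266 as stated. That figure is not affected here.

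**2. Model for the adverse reading.** Suppose that removal ends follow-up, or that later deaths are not counted. All rates below are assumptions, with constant hazards.

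- Annual death risk before removal, d: 5% or 10%; h0 = −ln(1 − d).
- Proportion removed in year 1 (in the absence of death), r: 20%, 40% or 60%; λ = −ln(1 − r).
- Death hazard ratio after removal, k: 1, 2 or 4; h1 = k·h0.
- Kaplan-Meier with censoring at removal: exp(−h0·t).
- True OS: S(t) = exp(−(h0+λ)t) + λ[exp(−h1·t) − exp(−(h0+λ)t)] / (h0 + λ − h1).

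**3. Middle case: d = 10%, r = 40%, k = 2.** h0 = 0.1054, λ = 0.5108, h1 = 0.2107, h0 + λ = 0.6162, denominator 0.4055.

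- 12 months: Kaplan-Meier 0.900. True OS = 0.5400 + 0.5108 × (0.8100 − 0.5400)/0.4055 = 0.880. Overstatement 2.0 points.
- 24 months: Kaplan-Meier 0.810. True OS = 0.2916 + 0.5108 × (0.6561 − 0.2916)/0.4055 = 0.751. Overstatement 5.9 points.

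**4. Full range.** Overstatement in percentage points, 12 months / 24 months:

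| Annual death risk | Removed in year 1 | k = 1 | k = 2 | k = 4 |
|---|---|---|---|---|
| 5% | 20% | 0 / 0 | 0.5 / 1.7 | 1.4 / 4.8 |
| 5% | 40% | 0 / 0 | 1.0 / 3.3 | 3.0 / 9.3 |
| 5% | 60% | 0 / 0 | 1.7 / 4.8 | 4.8 / 13.4 |
| 10% | 20% | 0 / 0 | 0.9 / 3.1 | 2.7 / 8.0 |
| 10% | 40% | 0 / 0 | 2.0 / 5.9 | 5.5 / 15.4 |
| 10% | 60% | 0 / 0 | 3.2 / 8.5 | 8.8 / 22.1 |

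**5. The planned follow-up runs and its deaths count.** Take removal as the last dose, and count deaths for 1 year after it. At 12 months nobody is more than 1 year past removal, so the bias is zero. For 24 months, Kaplan-Meier = exp(−∫h(u)du), with h(u) = [h0·P0(u) + h1·P1(u)]/[P0(u) + P1(u)]. Here P0(u) = exp(−(h0+λ)u), and P1(u) is the integral of λ·exp(−(h0+λ)v)·exp(−h1(u−v)) over v from max(0, u−1) to u. Numerical integration gives 76.05% against a true 75.08% in the middle case, a residual of 1.0 point. Over the whole grid the residual is 0 to 2.4 points.

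**The case against.** The strongest reply is that the context already resolves the wording. The second half of the Section 6.4 sentence says that patients with stable or responding GVHD continue treatment, so the contrast drawn is about treatment. Section 6.5 then lists the same three reasons as ends of treatment. The list in Section 5.4.3 is introduced as applying to the treatment period. Section 6.6.2 and footnote m cover these patients and do not stop for relapse, progression or toxicity. The censoring rule covers only patients who are alive; no rule censors at withdrawal or at the end of treatment. Section 11.3.4 provides case report form screens for progression deaths in survival follow-up.

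Most of this stands. A reader might infer that these deaths are in fact censored and that OS is biased as a matter of course. The documents do not support that, because they schedule follow-up of exactly these patients. Nor do they support the inference that relapse and new-therapy data are lost: footnote j calls for the relapse date and subsequent management, and footnote m for relapse and new GVHD therapy.

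What the reply does not remove is the conflict itself. Section 3.3 uses the discontinuation phrase of Section 6.4 for withdrawal of consent, which is a true study exit. Section 10.4.1 tabulates withdrawal from treatment and from the study, so the protocol recognises both. *On study* remains undefined, and Section 11.3.4 points to the narrower meaning.

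**Conclusion.** This is an ambiguity that can produce bias, not an established bias. An upward bias in OS needs two things: deaths after treatment stops must be uncollected or uncounted, and the death risk must be higher after removal than before.

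Under the assumed rates, the overstatement is 0 to about 9 points at 12 months and 0 to about 22 points at 24 months, and zero throughout when the hazard ratio is 1. The upper ends combine a 10% annual death risk, 60% removal in year 1 and a hazard ratio of 4. They are illustrations, not estimates for this trial. If the planned follow-up runs and its deaths count, the error on the same grid is nil at 12 months and at most 2.4 points at 24 months.

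The point should be fixed but is not critical. OS is a secondary endpoint described by a Kaplan-Meier curve, with no hypothesis test, and the primary response rate is not affected. It matters because follow-up lost when a site closes a patient out may not be recoverable at analysis.

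**What to change.** - **Sections 5.4.3 and 6.4:** reconcile them with Sections 3.3, 6.5 and 6.6.2, so that these patients stay in safety follow-up (6.6.1) and survival follow-up (6.6.2). Keep study exit for withdrawal of consent, loss to follow-up, death or study end. The edit concerns follow-up only and should not change when treatment stops.
- **Section 10.4.2:** define the OS event as death from any cause, including deaths in survival follow-up. State that stopping study treatment or starting new therapy is not a censoring event.

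The cost is wording in three sections. The quarterly contacts and the case report form screens for deaths in follow-up are already planned. The one downside for the sponsor is that reported OS may be less favourable.
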